7.1.5. Rechallenge

Study treatment restart or rechallenge after liver chemistry stopping criteria are met by any participant in this study is not allowed.

7.2. Participant discontinuation/withdrawal from the study

A participant may withdraw from the study at any time at the participant's own request for any reason (or without providing any reason).

A participant may be withdrawn at any time at the discretion of the investigator for safety, behavioral, or compliance reasons.

Investigators will attempt to contact participants who do not return for scheduled visits or follow-up.

At the time of discontinuing from the study, if possible, an ED visit should be conducted together with a follow-up visit approximately 18 days after the last dose of study intervention, as shown in the SoA. See SoA for data to be collected at the time of study discontinuation and follow-up and for any further evaluations that need to be completed. A participant who is withdrawn from the study for any reason related to safety (listed in Section [7.1](#) or otherwise) will continue to be followed up to assess the outcome of the safety event that triggered discontinuation of study drug. If a participant is unable to return to the clinic for any reason, site staff are encouraged to contact the participant for assessment of AEs.

The participant will be permanently discontinued from the study intervention and the study at that time.

All data and samples collected up to and including the date of withdrawal of/last contact with the participant will be included in the study analyses. If the participant withdraws consent for disclosure of future information, the sponsor may retain and continue to use any data collected before such a withdrawal of consent.

If a participant withdraws from the study, the participant may request destruction of any samples taken and not tested, and the investigator must document this in the site study records.

The primary reason for participant discontinuation/ withdrawal from the study will be documented in the eCRF based on the list below:

| Reasons | Additional items/Sub-reasons |
|--|--|
| AE | Unsolicited AE Solicited AE |
| Lost to follow-up | Subject Relocated Subject was Incarcerated Other, specify Unknown |
| Participant Reached Protocol-Defined Stopping Criteria | Liver Event QTc Laboratory Abnormality |
| Physician Decision | Loss of ability to freely provide consent due to treatment of either a psychiatric or physical condition |
| Pregnancy | |
| Protocol Deviation | Repeat non-adherence of participant with protocol requirements or treatment |
| Site Terminated by Sponsor | |
| Study Terminated by Sponsor | |
| Withdrawal by Participant | Burden of Procedure Participant Relocated Pursue Alternative Treatment COVID-19 Pandemic Other |
| Death | |

Participants who are withdrawn from the study because of AEs/SAEs must be clearly distinguished from participants who are withdrawn for other reasons. Investigator will follow participants who are withdrawn from the study due to an AE/SAE until the event is resolved (see Section 10.3.7.5).

7.3. Lost to follow-up

A participant will be considered lost to follow-up if the participant repeatedly fails to return for scheduled visits and is unable to be contacted by the study site.

The following actions must be taken if a participant fails to return to the clinic for a required study visit:

- The site must attempt to contact the participant and reschedule the missed visit as soon as possible, counsel the participant on the importance of maintaining the

assigned visit schedule and ascertain whether the participant wishes to and/or should continue in the study.

- Before a participant is deemed lost to follow-up, the investigator or designee must make every effort to regain contact with the participant (where possible, 3 telephone calls, and if necessary, a certified letter to the participant's last known mailing address or local equivalent methods). These contact attempts should be documented in the participant's medical record.
- Should the participant continue to be unreachable, the participant will be considered to have withdrawn from the study.
- Site personnel, or an independent third party, will attempt to collect the vital status of the participant within legal and ethical boundaries for all participants randomized, including those who did not get study intervention. Public sources may be searched for vital status information. If vital status of the participant is determined as deceased, this will be documented and the participant will not be considered lost to follow-up. Sponsor personnel will not be involved in any attempts to collect vital status information.

8. STUDY ASSESSMENTS AND PROCEDURES

- Study procedures and their timing are summarized in the SoA (Section 1.3). Protocol waivers or exemptions are not allowed.
- Immediate safety concerns should be discussed with the sponsor immediately upon occurrence or awareness to determine if the participant should continue or discontinue study intervention.
- Adherence to the study design requirements, including those specified in the SoA, is essential and required for study conduct.
- All screening evaluations must be completed and reviewed to confirm that potential participants meet all eligibility criteria. Subjects who have signed informed consent but are not eligible to proceed should be recorded in the eCRF with a status of 'screen failure'.
- Procedures conducted as part of the participant's routine clinical management (e.g., blood count) and obtained before signing of the ICF may be utilized for screening or baseline purposes provided the procedures met the protocol-specified criteria and were performed within the timeframe defined in the SoA.
- In the event of a significant study-continuity issue (e.g., caused by a pandemic), alternate strategies for participant visits, assessments, study intervention distribution and monitoring may be implemented by the sponsor or the investigator, as per local health authority/ethics requirements.
- Safety/laboratory/analyte results that could unblind the study will not be reported to investigative sites or other blinded personnel until the study has been unblinded.

- The maximum amount of blood collected from each participant over the duration of the study, including any extra assessments that may be required, will not exceed 500 mL within 56 days.
- Repeat or unscheduled samples may be taken for safety reasons or for technical issues with the samples.

8.1. Administrative and general/baseline procedures

8.1.1. Collection of demographic data

Record demographic data such as date of birth (month and year), sex, race, and ethnicity in the participant's eCRF.

Collection of sex, race and ethnicity data is necessary to assess and monitor the diversity of the trial participants, and to determine if the trial participants are truly representative of the impacted population.

8.1.2. Medical history

Obtain the participant's medical history by interviewing the participant and/or review of the participant's medical records. Record any pre-existing conditions, signs and/or symptoms present prior to the first dose of study intervention in the eCRF.

Any condition meeting the criteria of a SAE that occurs after signing the ICF but before the first dose of study intervention should be reported as described in Section 8.4.

8.2. Efficacy assessments

Planned timepoints for all efficacy assessments are provided in the SoA (Section 1.3).

8.2.1. HIV-1 RNA Sampling

Plasma for quantitative HIV-1 RNA will be generated at timepoints listed in the SoA (Section 1.3).

An HIV-1 RNA PCR assay with a LLOD of 40 copies/mL or lower will be used.

Details concerning the handling, labeling, and shipping of these samples will be provided in the laboratory manual.

In order to maintain the blind, HIV-1 RNA results will not be provided to site staff.

8.2.2. Lymphocyte Subsets by Flow Cytometry

Blood samples will be obtained from each participant for the analysis of lymphocyte subsets by flow cytometry at the timepoints listed in the SoA (Section 1.3).

Details concerning the handling, labeling and shipping of these samples will be provided in the laboratory manual.

8.2.3. Disease Progression

HIV-associated conditions will be recorded as per the SoA (Section 1.3).

CDC-classification will be assessed according to the 2014 CDC Revised Classification System for HIV Infection in Adults (See Section 10.9).

8.3. Safety assessments

Planned timepoints for all safety assessments are provided in the SoA (Section 1.3).

8.3.1. Physical examination

- A complete physical examination will include, at a minimum, assessments of the CV, respiratory, gastrointestinal, and neurological systems. A brief physical examination will include, at a minimum, assessments of the skin, lungs, CV system, and abdomen.
- Investigators should pay special attention to clinical signs related to previous serious illnesses.
- Height and weight will also be measured and recorded. Height will be captured at Screening only. Weight will be captured at each visit to accurately calculate BMI and eGFR. For guidance on weight measurement see Section 8.3.1.1.

8.3.1.1. Weight measurement

Adapted from WHO STEPS Surveillance Manual [[WHO](#), 2017]

Equipment

To measure weight, you will need a weighing scale, (such as a SECA scale or the Tanita HS301 Solar Scale). Alternatively, a BMI scale measuring both height and weight (e.g., Growth Management Scale) can be used.

Ensure the scale has been regularly calibrated according to the manufacturer instructions and that calibration documentations are filed and available to the study CRA as required.

We recommend using the same scale across visits for individual study participants.

We recommend having the same study staff performing the measurement across visits for individual study participants.

We recommend that the time of day a participant's weight is measured is consistent for every participant at the site within the study (e.g., If measured at 10 am at initial measurement, attempt to have the participant measured at 10 am at subsequent visits).

Set up requirements

Make sure the scales are placed on a firm, flat surface. Do not place the scales on:

- carpet

- a sloping surface
- a rough, uneven surface.

Set up scales

Follow the steps below before measuring the weight of a participant:

1. Make sure the scale is on a firm, flat surface.
2. Turn on the scale and wait until the display shows 0.0.

Procedures

Follow the steps below to measure the weight of a participant:

1. Ask the participant to remove their footwear (shoes, slippers, sandals, etc). They should also take off any heavy belts and remove all objects out of their pockets (example: mobile phones, wallets, coins).
2. Ask the participant to step onto scale with one foot on each side of the scale.
3. Ask the participant to:
 - stand still
 - face forward
 - place arms on the side and
 - wait until asked to step off.
4. Record the weight in **kilograms to one decimal place** in the eCRF.

8.3.2. Vital signs

Oral temperature, pulse rate, respiratory rate, and blood pressure will be recorded (before blood collection for laboratory tests).

Blood pressure and pulse measurements will be assessed in semi-supine position with a completely automated device. Manual techniques will be used only if an automated device is not available.

Blood pressure and pulse measurements will be preceded by at least 5 minutes of rest for the participant in a quiet setting without distractions (e.g., television, cell phones). 3 consecutive blood pressure and pulse readings will be recorded at intervals of at least 1 minute. The first reading should be rejected. The average of the second and third readings should be recorded.

8.3.3. Electrocardiograms

See [Table 7](#) and [Table 8](#) in Section [8.5](#).

TriPLICATE and Single 12-lead ECGs will be obtained as outlined in the SoA (see Section [1.3](#)) using an ECG machine that automatically calculates the heart rate and measures PR, QRS, QT, and QTcF intervals. Refer to Section [7.1.2](#) for QTcF withdrawal criteria and any additional QTcF readings that may be necessary.

At each timepoint at which triplicate ECGs are required, 3 individual ECG tracings should be obtained as closely as possible in succession, but no more than 2 minutes apart. The full set of triplicates should be completed in less than 4 minutes.

8.3.4. Clinical safety laboratory tests

See Section 10.2 for the list of clinical laboratory tests to be performed in accordance with lab manual and the SoA (Section 1.3).

The investigator must review the laboratory results, document this review, and record any clinically significant changes occurring during the study as an AE. The laboratory results must be retained with source documents.

Abnormal laboratory findings associated with the underlying disease are not considered clinically significant unless judged by the investigator to be more severe than expected for the participant's condition.

All laboratory tests with values considered clinically significantly abnormal during participation in the study or within 28 days after the last dose of study intervention should be repeated until the values return to normal or baseline or are no longer considered clinically significant by the investigator or medical monitor.

- In the absence of a diagnosis, abnormal laboratory findings, assessments or other abnormal results the investigator considers clinically significant will be recorded as an AE or SAE, if they meet the definition of an AE or SAE (refer to Section 10.3.1 and Section 10.3.2).
- If clinically significant values do not return to normal/baseline within a period of time judged reasonable by the investigator, the etiology should be identified, and the sponsor notified.
- If laboratory values from non-protocol-specified laboratory tests performed at the institution's local laboratory require a change in participant management or are considered clinically significant by the investigator (e.g., SAE or AE or dose modification), then the results must be recorded.

Refer to the laboratory manual for appropriate processing and handling of samples to avoid duplicate and/or additional blood draws.

- All study-required laboratory assessments will be performed by a central laboratory, with the exception of Screening laboratory assessments which may be performed at the local laboratory in exceptional circumstances, if this more readily facilitates evaluation of the eligibility of candidate study participants. The Investigator will review the local laboratory reports, confirm eligibility and document this in the eCRF (see Section 10.2). At the Screening site visit, the scheduled laboratory assessments should also be collected for analysis by the central laboratory. NOTE: For eligible participants on Study Day 1, all laboratory assessments should be repeated and performed by the central laboratory as described in the SoA (See Section 1.3).
- From Day 1 onwards, local laboratory results are only required in the event that the central laboratory results are not available in time for either a treatment and/or response evaluation to be performed. If a local sample is

required, it is important that the sample for central analysis is obtained at the same time. Additionally, if the local laboratory results are used to make either a treatment or a response evaluation or are considered clinically significant by the investigator (e.g., SAE or AE) the results must be entered in the eCRF.

8.3.5. Pregnancy testing

Participants who were female at birth are only eligible to participate if they are confirmed to be a PONCBP as defined in Section 10.4.

8.3.6. Suicidal ideation and behavior risk monitoring

VH3739937 is not a central nervous system active drug nor is it being developed for a neurologic or psychiatric condition. However, given the risk of suicidal ideation at supratherapeutic doses identified in one study with another MI, GSK3532795, all participants will undergo assessment for suicidality in this study. Any clinically diagnosed case of suicidality (using the C-SSRS as tool during Screening, on-treatment, and in follow-up) will result in exclusion from the trial or (if already randomized) immediate discontinuation from the study. Moreover, in these cases, the Investigator will arrange for urgent psychiatric evaluation and management.

Participants with HIV infection occasionally may present with symptoms of depression and/or suicidality (suicidal ideation or behavior). In addition, there have been some reports of depression, suicidal ideation and behavior (particularly in patients with a pre-existing history of depression or psychiatric illness) in some patients being treated with other ARTs such as INSTIs, including DTG. Therefore, it is appropriate to monitor participants for suicidality before and during treatment.

Participants being treated with VH3739937 should be monitored appropriately and observed closely for SIB or any other unusual changes in behavior, especially at the beginning and end of the course of intervention, or at the time of dose changes, either increases or decreases. Participants who experience signs of SIB should undergo a risk assessment. All factors contributing to SIB should be evaluated and consideration should be given to discontinuation of the study intervention. It is recommended that the investigator consider mental health consultation or referral for participants who experience signs of suicidal ideation or behavior. Participants presenting with new onset/treatment emergent depression should be advised to contact the investigator immediately if symptoms of severe acute depression (including suicidal ideation/attempts) develop, because medical intervention and discontinuation of the study medication may be required.

When informed consent has been given, families and caregivers of participants being treated with VH3739937 should be alerted about the need to monitor participants for the emergence of unusual changes in behavior, as well as the emergence of SIB and to report such symptoms immediately to the study investigator.

Baseline assessment of SIB and intervention-emergent suicidal ideation and behavior will be monitored during this study using the C-SSRS. The definitions of behavioral suicidal events used in this scale are based on those used in the Columbia Suicide History Form

[Posner, 2007]. Questions are asked on suicidal behavior, suicidal ideation, and intensity of ideation. Day 1 (Baseline) visit questions will be in relation to lifetime experiences and current experiences (within the past 2 months); all subsequent questioning is in relation to the last assessment. The C-SSRS is to be administered by a clinician at the timepoints specified in the SoA (Section 1.3). The C-SSRS will be conducted electronically by computer/tablet connected to the internet.

Additionally, the investigator will collect information using the PSRAE eCRF form in addition to the AE (non-serious or SAE) eCRF form on any participant that experiences a possible suicidality-related AE while participating in this study. This may include, but is not limited to, an event that involves suicidal ideation, a preparatory act toward imminent suicidal behavior, a suicide attempt, or a completed suicide. The investigator will exercise their medical and scientific judgment in deciding whether an event is possibly suicide-related. PSRAE forms should be completed and reported to GSK/ViiV Healthcare within 1 week of the investigator diagnosing a possible suicidality-related AE.

As described in Section 7.1.3, new onset suicidal ideation of concern to the Investigator (see below) at any time will result in immediate discontinuation from the study and the Investigator will arrange for urgent specialist psychiatric evaluation and management.

Emergent non-suicidal Psychiatric AE Evaluation and Management:

- Any Grade 1 or 2 Psychiatric AE: A Grade 1 or 2 Psychiatric AE may result in additional unscheduled visits (in-clinic or at home) as clinically indicated. This may include a more in-depth assessment of AE through interview, additional unscheduled clinical labs, and/or imaging. Psychiatric consultation may be required at the discretion of the Investigator. Any pharmacotherapy should be discussed with the Medical Monitor.
- Any Grade 3 or 4 Psychiatric AE: As described in Section 7.1.3, a Grade 3 or 4 Psychiatric AE will result in discontinuation from the study and emergency psychiatric evaluation (including potential hospitalization and pharmacotherapy as indicated). A urine sample should be submitted for the Drugs of Abuse panel.

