| | | | | | | | | | | | | | 55 years in first degree relatives only See Section 8.1.2 for more information |
| Prior ART check to ensure naïve status | X | | | | | | | | | | | | |
| CDC classification | X | X | | | | | | | | | | | See Section 8.2 for more information |
| HIV-associated conditions | X | X | X | X | X | X | X | X | X | X | X | | See Section 8.2 for more information |
| Plasma for HIV-1 genotype/phenotype ⁴ | | X | X | X | | X | | X | X | X | X | | See Section 8.8 for more information |
| HIV-1 RNA | X | X | X | X | | X | | X | X | X | X | X | See Section 8.2 for more information |
| Physical examination including height and weight ⁵ | X | X | | | | | | X | | | | X | See Section 8.3.1 for more information |
| Vital signs | X | X | X | X | | X | | X | X | X | X | X | See Section 8.3.2 for more information |
| C-SSRS Administration | X | | | | | | | X | | | | X | See Section 8.3.6 for more information |
| ECG: single reading | X | | | | | | | | | | | | See Section 8.3.3 for more information |

CONFIDENTIAL

212580

Protocol Amendment 1 Final

| Procedure ¹ | Screening ² (7-14 days before Day 1) | Study Intervention Period Days 1-7 | | | | | | Post-Study Intervention Follow-up Days 8-21 | | | Follow-up/ED ¹⁵ | Notes ED = early discontinuation/withdrawal | |
|---|--|------------------------------------|----------------|---|-----------------------|---|-----------------------|---|----------------|-----------------------|----------------------------|--|---|
| | | Day 1 | Day 2 | Days 3 and 4 1 clinic visit and 1 virtual ³ | | Days 5 and 6 1 clinic visit and 1 virtual ³ | | Day 7 | Day 8 | Day 14 (+/- 1 day) | Day 21 (+/- 1 day) | | |
| | | Clinic visit 1 | Clinic visit 2 | Clinic visit 3 | Virtual ¹⁴ | Clinic visit 4 | Virtual ¹⁴ | Clinic visit 5 | Clinic visit 6 | Clinic visit 7 | Clinic visit 8 | Clinic visit 9 | |
| ECG: single reading pre-dose ¹³ | | | X | X | | X | | X | X | | | X | See Section 8.3.3 for more information |
| ECG: triplicate reading pre-dose | | X | | | | | | | | | | | See Section 8.3.3 for more information |
| ECG: single reading post-dose at 5, 7, 8 and 9 h | | X | | | | | | X ⁶ | | | | | See Section 8.3.3 for more information |
| Confirmation of PONCBP (female participants) | X | | | | | | | | | | | | See Section 10.4.1.1 for more information |

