| Single pre-dose PK sample ¹³ | | | X | X | | X | | X | X | X | X | X | See Section 8.5 for more information |

The timing of planned study assessments may change during the course of the study based on emerging data/in-stream data review (e.g., to obtain data closer to the time of peak plasma concentrations) to ensure appropriate monitoring.

The CA and IEC will be informed of any safety issues that constitute a substantial amendment and require alteration of the safety monitoring scheme or amendment of the ICF. The changes will be approved by the CA and the IEC before implementation.

1. Order of procedures (pre-dose): C-SSRS – ECG – Vital Signs – Blood Draws to allow the blood draw to occur as close as possible to the nominal time (See Section 8.5 for further information regarding order of blood draw and ECG during Clinic Visits 1 and 5 [Study Days 1 and 7]).
2. Participants will be randomized within approximately 7 to 14 days of the start of Screening but may be extended up to 28 days maximum. Screening laboratory assessments may be performed at the local laboratory in exceptional circumstances, if this more readily facilitates evaluation of the eligibility of potential study participants. The Investigator will review the local laboratory reports, confirm eligibility and document this in the eCRF. At the Screening site visit, the scheduled laboratory assessments should also be collected for analysis by the central laboratory.
3. Participants who pass screening will be required to attend 9 in-clinic outpatient visits. Flexibility is offered for Clinic Visits 3 and 4 which may take place on either Study Day 3 or Day 4 (Clinic Visit 3), or on Study Day 5 or Day 6 (Clinic Visit 4), with a virtual visit to be conducted on the non-clinic day. The visit schedule for each participant will be pre-planned to be sure weekend, work schedules and clinic hours are appropriately considered. In particular, Clinic Visits 1 and 5 (Study Days 1 and 7) must be scheduled on days when participants and site staff will be able to complete serial PK sampling up to 12 h post-dose.
4. Genotypic/Phenotypic testing will be conducted on Day 1 and Day 8 samples, with samples collected at other visits tested as appropriate.

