7.1.3. Individual Participant Laboratory Abnormality and Adverse Event Stopping Criteria

Investigators should make every effort to have a discussion with the Medical Monitor before the next dose to help assess if the study intervention should be stopped. Individual participant laboratory abnormality and AE stopping criteria for the study, as follows:

| | |
|---------------|---|
| Adverse Event | 
 Any clinically significant AE deemed to require discontinuation of the IP Any related Grade 3 or any Grade 4 rash Grade 2 rash with evidence of systemic involvement Grade 2 or higher rash with concurrent fever, AST/ALT elevation or eosinophilia prior to the follow up phase will be withdrawn from study intervention Grade 3 or higher allergic reaction Any Grade 3 or higher Psychiatric AE. The investigator will discontinue the participant from the study and arrange for emergency psychiatric evaluation/management; the panel for drugs of abuse will be tested New onset suicidal ideation as clinically diagnosed by the Investigator (in consultation with psychiatry, if needed). The Investigator will discontinue the participant from the study and arrange for emergency specialist psychiatric evaluation/management Any Grade 3 or higher AE related to study medication Any Grade 4 AE or laboratory abnormalities (with the exception of an asymptomatic grade 4 cholesterol, triglyceride or CPK increase) A participant meets the QTcF stopping criteria described in Section 7.1.2 Moderate to severe (as clinically determined by the investigator) COVID-19 infection (suspect, probable, or confirmed using the most recent version of the WHO case definition) |
|---------------|---|

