**Suicidality Score**

Baseline suicidality data assessed electronically via the C-SSRS questionnaire will be summarised. Number and percentage of participant with suicidal ideation or behaviour during lifetime and currently (i.e. within the past 2 months of screening) will be presented.

Post baseline (and baseline) participant-level suicidality data will be available via RAPIDO DV.

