#### 6.3.4. Multiple measurements at One Analysis Time Point

If ECG has been assessed more than once (e.g. in triplicate) at an analysis time point, the average of the available ECG measurements will be calculated and summary statistics will be based on the calculated average. This applies to both baseline and post baseline assessments.

For lab tests on a study day, if more than one assessment is taken on the same day, the test from a central lab will be taken over the test from a local lab. If multiple assessments are taken from the same type of lab on a study day, the worst case will be used.

Other Safety Endpoints
Columbia Suicide Severity Rating Scale (C-SSRS)

• Missing data will not have any imputation performed.

• A positive alert is triggered if a subject has reported suicidal ideation/behaviour in categories 4-9.

• Questions in categories 3-5 will be triggered if suicidal ideation is reported in categories 1 or/and 2.

• Incomplete calls:

○ when no complete call is databased on the same day, the data from the incomplete call will be used

Other Safety Endpoints	
Columbia Suicide Severity Rating Scale (C-SSRS)	
	
 
○ if a subject has only an incomplete call, and it resulted in a positive alert, the relevant pages in the CRF should be completed, even though the call was incomplete
 
○ when a complete call is databased on the same day, the data from the complete call will be used in the summaries.
 
● Duplicate calls, 
 
○ if they occur on the same day: 
 
■ Both calls will be reported in the listings.
 
■ For summary tables, the entry with latest time record will be used.
 
■ For summary tables at baseline, unscheduled repeat visits will not be summarised.
 
■ Relevant CRF pages will be completed based on the latest entry (if it was a positive alert).
 
 
 
○ If they occur on different days 
 
■ take the entry closest to the target visit date
 
 
 
 
 
● Visit 1 (Screening) assessments performed after study treatment initiation will not be included in Baseline summaries
 

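### Protocol 8.3.6 sets the C-SSRS baseline at Day 1, but the schedule has no Day 1 C-SSRS and SAP 4.5.2 uses screening, so at least half of the first post-dose look-back is before dosing

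*Protocol*

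**What the plan says.** - **Protocol 8.3.6** gives the baseline visit and its reference period: "Day 1 (Baseline) visit questions will be in relation to lifetime experiences and current experiences (within the past 2 months". For every administration after that, "all subsequent questioning is in relation to the last assessment". It then defers to the schedule for timing: "The C-SSRS is to be administered by a clinician at the timepoints specified in the SoA (Section 1.3".
- **Protocol 1.3 (SoA)**, row "C-SSRS Administration", carries three marks: Screening, one visit at the end of the seven-day intervention period, and the Day 25/early discontinuation visit. The Day 1 cell is empty. Screening is planned 7 to 14 days before Day 1, "but may be extended up to 28 days maximum".
- **SAP 4.5.2 (Suicidality Score)** takes the baseline summary from screening: the number and percentage with "suicidal ideation or behaviour during lifetime and currently (i.e. within the past 2 months of screening) will be presented". After baseline it plans no C-SSRS table; those data go to a participant-level viewer.
- **SAP 6.3.4** adds: "Visit 1 (Screening) assessments performed after study treatment initiation will not be included in Baseline summaries". This label is ambiguous. In the SAP 6.3.3 window table, Visit 1 is Study Day 1, and in the SoA, Clinic visit 1 is also Day 1.
- **Protocol 7.1.3** lists as an individual stopping criterion: "New onset suicidal ideation as clinically diagnosed by the Investigator".

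**The concern.** Protocol 8.3.6 says that the C-SSRS is there to monitor suicidal ideation and behaviour that emerges on the intervention. A questionnaire that asks about the time since the previous form can do this cleanly only if the previous form was completed just before the first dose. A Day 1 form would provide that. If the SoA is followed, the previous form is the one from Screening, one to four weeks earlier, and a positive answer at the end of the intervention period does not by itself say whether the ideation began before or after dosing.

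Neuropsychiatric safety is one of the potential class risks named in Protocol 2.3. Adverse events that lead to discontinuation up to Day 8 form part of a secondary endpoint, and active cohorts have about 6 participants. Attribution of a single event would therefore be visible in the results. There is also a detection aspect: ideation that begins after Screening may not be picked up by the instrument until the end of the intervention period.

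**Working it through.** **1. Is the empty Day 1 cell reliable?** The C-SSRS row has 12 cells, with marks in cells 1, 8 and 12. The physical examination row has marks in cells 1, 2, 8 and 12, so cell 2 is Day 1 and it is blank for the C-SSRS. Cell 8 reads as Day 7. That column is less secure: the fasting lipid row is also marked in cell 8, while SoA note 7 gives Day 8 for that test. The table may have shifted in extraction, so both days are computed below.

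**2. Check of the Screening gap against the plan's own figure.** Protocol 4.1 gives total participation of about 32 to 53 days. With gaps of 7 and 28 days: 7 + 7 + 18 = 32 and 28 + 7 + 18 = 53. Both reproduce.

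**3. Look-back of the first post-dose form under the SoA.** Let g be the days from Screening to Day 1 and d the study day of the form.

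Look-back = g + (d − 1). Pre-dose share = g / [g + (d − 1)].

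| Gap g (days) | Form on Day 7: look-back | Pre-dose share | Form on Day 8: look-back | Pre-dose share |
|---|---|---|---|---|
| 7 | 7 + 6 = 13 | 7/13 = 54% | 7 + 7 = 14 | 7/14 = 50% |
| 14 | 14 + 6 = 20 | 14/20 = 70% | 14 + 7 = 21 | 14/21 = 67% |
| 28 | 28 + 6 = 34 | 28/34 = 82% | 28 + 7 = 35 | 28/35 = 80% |

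**4. Look-back if a pre-dose Day 1 form is given, as 8.3.6 describes.** It is 6 days (Day 7) or 7 days (Day 8), with a pre-dose share of 0%.

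**5. What the SAP would use as baseline.** The general rule in SAP 4.1.2 takes the last available value before dosing. With no Day 1 form scheduled, that is normally the Screening form. If a Day 1 pre-dose form were given, the same rule would pick it, and SAP 4.5.2 would then describe the wrong visit.

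**6. Where an error could enter the results.** Because no post-baseline C-SSRS table is planned, the route is through adverse event and discontinuation tables. Two SAP date rules lean towards treatment when onset is unclear. Under 6.3.5, an event with a missing start day in the month of first dose is set to the first-dose date, unless a full stop date falls earlier. Under 6.3.1, an untimed adverse event on Day 1 is taken as after dosing.

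**7. Scale of one case, as illustration only.** One participant in a cohort of 6 is 1/6 = 16.7% (exact 95% CI 0.4% to 64.1%). The documents give no event rate, so this says how much one misattributed case would weigh, not how likely it is.

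**The case against.** The strongest reply is that 8.3.6 already hands timing to the SoA, SAP 4.5.2 agrees with it, and only a visit label in 8.3.6 needs correcting. On timing alone this is fair. It does not settle the reference period: 8.3.6 still defines the lifetime and two-month questions for a visit with no form, and nothing states that the first post-dose form reaches back to Screening.

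Several safeguards also stand and narrow the consequence:

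- Screening includes a C-SSRS, exclusion criterion 3 covers suicidality, and the SoA requires eligibility and clinical status to be rechecked on Day 1 before the first dose. A reader might infer that there is no pre-dose assessment at all; that is not so.
- Under Protocol 8.4.1 and SAP 6.1.5, events that begin after consent but before dosing are medical history. Protocol 10.3.6 requires a treatment-emergent event to be absent or milder beforehand. Misattribution therefore needs an onset date that is unclear or was not asked for.
- A clinician administers the form and can ask about onset.

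A reader might also infer that the mismatch itself causes participants to be stopped. The documents do not support this. Section 8.3.6 discontinues any randomized participant with clinically diagnosed suicidality, whenever it began, and the criterion in 7.1.3 rests on the investigator's diagnosis, not on the form's baseline.

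**Conclusion.** The inconsistency is real: 8.3.6 puts the baseline at Day 1, the SoA schedules no form there, and SAP 4.5.2 uses screening. SAP 6.3.4 does not resolve it, because its visit label fits either reading. If the SoA is followed, at least half of the time covered by the first post-dose form precedes the first dose: 54% to 82% for Day 7, 50% to 80% for Day 8. This rests on the stated 7 to 28 day Screening gap and on later questions running from the previous form.

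The consequence is limited to two things. Ideation with an unclear onset can be attributed to treatment in the adverse event and discontinuation tables, and ideation arising after Screening may not be captured by the C-SSRS until the end of the intervention period, although the Day 1 clinical recheck may find it. The percentages should not be read as probabilities of misattribution. The point is worth correcting for clarity of attribution; it does not change who is discontinued.

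**What to change.** Reconcile Protocol 8.3.6, the SoA row, SAP 4.5.2 and SAP 6.3.4 to one pre-dose C-SSRS baseline visit and one reference period for the first post-dose form. The sponsor should say which was intended:

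- **If 8.3.6 is intended:** add a Day 1 pre-dose mark to the SoA row, and have the SAP use that form as baseline.
- **If the SoA is intended:** correct the visit in 8.3.6, state that the first post-dose form covers the time since Screening, and record onset relative to first dose for any positive answer.

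In either case, replace the Visit 1 label in SAP 6.3.4 with an unambiguous visit name, confirm whether the middle form falls on Day 7 or Day 8, and state the expected number of forms for the compliance measure in SAP 6.2.1 (3 for a completer under the SoA; 4 if a Day 1 form is added to Screening).

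The cost is wording in two documents and at most one short form at a visit already attended. The SAP records that the Part 1 interim has taken place, so a schedule change could reach only participants not yet dosed; for the others, the SAP can state which form served as baseline.
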